#### **5.2 Exclusion criteria.**

##### Case group:

- 1) Infertility due to malformation of reproductive tract
- 2) Infertility caused by endocrine factors such as polycystic ovary syndrome,

premature ovarian failure and severe hyperthyroidism

- 3) Infertility due to male factors
- 4) Patients with malignant tumors
- 5) Patients with autoimmune diseases
- 6) Patients with severe heart, kidney and other basic diseases
- 7) Patients who consumed antibiotics 3 days before the examination
- 8) Have the habit of smoking and drinking

Control group:

- 1) Pregnancy by various assisted reproductive means
- 2) Patients with malignant tumors
- 3) Patients with autoimmune diseases
- 4) Patients with severe heart, kidney and other basic diseases
- 5) Patients who consumed antibiotics 3 days before the examination
- 6) Have the habit of smoking and drinking

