#### **Case group:**

- 1) Female aged 18-40
- 2) Regular menstrual cycle
- 2) Conform to the clinical diagnosis of infertility
- 3) No sexual life 3 days before the examination

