#### **control group:**

- 1) Female aged 18-40
- 2) Regular menstrual cycle
- 3) Patients who did pre-pregnancy consultation in our hospital, pregnant at the time of 3-month follow-up
- 4) No sexual life 3 days before the examination

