10.2 MALDI-TOF MS test results were recorded as: microbial type, positive, negative

## 11. Security evaluation

This study involves only 1 vaginal and cervical secretion collection, which is consistent with HPV sampling during cervical screening in routine clinical testing and does not cause additional collection points or additional consultation costs, and is safe. It may cause pain and a little bleeding to the patient, neither of which will have any impact on the patient's health. Inform the patient before the operation to avoid causing panic. If the patient has intercourse immediately after the test or performs inappropriate transvaginal operations that may lead to infection, the patient is advised to avoid intercourse, sitz baths and other transvaginal operations without professional medical guidance for 3 days after sampling.

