### 11.2 Adverse Events

(List of possible adverse events, all possible adverse reactions in the study should be fully considered, and should include possible adverse reactions in all aspects of laboratory tests (e.g. blood collection, ECG, imaging, etc.), interventions (e.g. drug treatment, surgical treatment, etc.) and other non-interventions (e.g. postural tests, scale tests, questionnaires, etc.), and evaluate the severity of the adverse reactions . (The same should also be reflected in the informed consent form, fully informed to the subject.)

Pain: pain can be graded (0-4),  $\geq 1$  noted as an adverse event

Grading: Grade 0: No pain.

Grade 1 (mild pain): painful but not severe, tolerable, sleep is not affected

Grade 2 (moderate pain): pain is obvious and unbearable, sleep is disturbed,

analgesics are requested

Grade 3 (severe pain): severe pain, unbearable sleep severely disturbed, analgesics needed

Bleeding: small amount 0.1-1ml, medium amount 1-5ml, large amount >5ml, medium and large amount of bleeding recorded as adverse events

Infections.

Mild infection - increased cervical or vaginal discharge, white belt routine indicating cleanliness grade III or leukocytes +++

Moderate - Large amount of discharge with abnormal characteristics, white belt routine indicating cleanliness IV or white blood cells ++++ or BV positive

Severe - with pain or pressure and the presence of infection are recorded as adverse events

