### 11.3 Pre-assessment of relevant risks and disposal plans

Pain:  $\geq$  grade 1 may be given pain medication

Bleeding: Vaginal gauze is used to stop heavy bleeding

Infection: mild infection - vaginal douching; moderate - vaginal medication based on routine leucorrhoea test results; severe - vaginal medication combined with oral anti-infection therapy based on routine leucorrhoea test results

\*The study sponsor will bear all the costs related to the above adverse events and exempt the subjects from the costs related to the adverse events, including all the costs related to the adverse events during and after the end of the trial.

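### The pre-sampling restrictions cover only intercourse and 'consumed' antibiotics, so recent non-antibiotic vaginal medication, douching or a transvaginal procedure neither excludes nor defers a woman and is not a named item on the data form

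*Combined protocol and SAP*

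**What the plan says.** Section 5.1 requires, for cases, "No sexual life 3 days before the examination", and repeats this for controls. Section 5.2 excludes, in both groups, "Patients who consumed antibiotics 3 days before the examination". The Program Summary says the same. These are the only time-limited restrictions before sampling. The exit criteria (5.3) and the sampling and storage steps (8.2.3, 8.3) add none in the text available.

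Other sections deal with local treatment and procedures:

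- Section 11.3 plans for infection as an adverse event: "mild infection - vaginal douching; moderate - vaginal medication based on routine leucorrhoea test results".
- Section 11.2 grades such infection partly by vaginal findings; the moderate grade includes "white belt routine indicating cleanliness IV or white blood cells ++++ or BV positive".
- Section 1.2 states that most women clear lower genital tract pathogens, by themselves or through drug treatment.
- Section 11 warns of a patient who "performs inappropriate transvaginal operations that may lead to infection", and so "the patient is advised to avoid intercourse, sitz baths and other transvaginal operations without professional medical guidance for 3 days after sampling".

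The 8.2.2 form lists confounders such as age, weight, obstetric history, menstrual dates and infertility diagnoses. It does not name recent vaginal medication, douching or procedures, though the list is open-ended.

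**The concern.** Part II relates pathogen status and CST to infertility, and both are read from one collection per woman (section 11). The two existing restrictions show that the sponsor wants recent exposures kept out of that sample, but the list is short. Under the written criteria, a woman who used a vaginal antifungal or antiseptic, or douched, the evening before would be enrolled and swabbed.

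If local treatment suppresses a pathogen or alters the flora, her exposure is misclassified. If this is equally common in both groups, the association is blurred. If it is more common in one group, the association can be pushed either way. Because the form does not name these exposures, no variable that the plan specifies would let the analyst examine the effect.

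**Working it through.** **What is covered before the swab, and what the protocol says of each exposure elsewhere**

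| Exposure in the previous 3 days | Restricted before the swab? | What the protocol says elsewhere |
|---|---|---|
| Intercourse | Yes (5.1) | Also to be avoided for 3 days after the swab (11) |
| Oral or other systemic antibiotic | Yes (5.2), at least if swallowed | Drug treatment can clear pathogens (1.2) |
| Vaginal antibiotic | Only if *consumed* means *used* | Vaginal medication treats infection (11.3) |
| Other vaginal medication | No | Vaginal medication treats infection (11.3) |
| Vaginal douching | No | Treats mild infection (11.3) |
| Transvaginal procedure | No | Infection risk, stated only for the period after the swab (11) |

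The inference that the exposure bears on the measurement is strong for vaginal medication and douching, because the protocol uses them against infection at the sampled site. It is weaker for procedures, which section 11 mentions only as a safety matter after sampling.

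**Could it differ by group?** Only the case exit criteria (5.3) mention an intraoperative finding. Controls come from pre-pregnancy consultation (5.1). A difference is plausible, but no figure is given, and neither is the timing of any operation relative to the swab.

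**Illustration of the mechanism.** The documents contain no figure to reproduce here. All inputs in the next table are assumptions. Let *p* be true exposure, *t* the share of the group recently treated and *e* the share of exposures that treatment hides. Observed exposure = *p*(1 − *t·e*).

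Assume *p* = 0.35 in cases and 0.20 in controls. The true odds ratio is (0.35/0.65)/(0.20/0.80) = 2.15.

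| *t* cases, *t* controls, *e* | Observed cases | Observed controls | OR |
|---|---|---|---|
| 0.20, 0.05, 0.5 | 0.35 × 0.90 = 0.315 | 0.20 × 0.975 = 0.195 | 1.90 |
| 0.20, 0.05, 1 | 0.35 × 0.80 = 0.280 | 0.20 × 0.95 = 0.190 | 1.66 |
| 0.40, 0.05, 1 | 0.35 × 0.60 = 0.210 | 0.20 × 0.95 = 0.190 | 1.13 |

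With no true difference (*p* = 0.35 in both groups), observed control exposure is 0.34125, 0.3325 and 0.3325, and the odds ratios are 0.89, 0.78 and 0.53.

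**The same formula with the rates in 6.1.2.** Assume 5–30% of cases treated, 50–100% of their positives hidden, and no controls treated. Case positivity then falls by a relative 2.5% (0.05 × 0.5) to 30% (0.30 × 1).

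- Rates as printed, 0.46% against 0.01%: the odds ratio falls from 46 to between 45 and 32.
- The same figures read as proportions, 0.46 and 0.01: case positivity falls to between 0.449 and 0.322, and the odds ratio from 84 to between 81 and 47.

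So the result runs from slight attenuation to near-disappearance of the association, or to an apparent protective effect where none exists, depending entirely on the inputs. The model covers masking only. Flora disturbed by douching or a procedure could move the result the other way.

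**The case against.** The case against giving this much weight is substantial, and most of it stands.

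- **Flora.** A reader might infer that the protocol itself says these exposures change the flora. It does not. Section 11.3 is an adverse-event plan and section 11 is safety advice after sampling, which need not match a measurement washout. The link is an inference.
- **Group difference.** A reader might infer that cases have been under infertility care for 2 years and so receive more local treatment. Section 6.2 gives 2 years as the duration of infertility, not of care, and no section reports treatment frequency in either group.
- **Wording.** The text reads as a translation, and *consumed* may mean *used*. That would cover vaginal antibiotics, but not other vaginal products, douching or procedures.
- **Irreparable harm.** A reader might infer that nothing could be corrected later. The 8.2.2 list is open-ended, the form is not reproduced, and the extracted text of 8.2.3 begins at its fourth step. What can be said is that no named variable supports adjustment.
- **Size.** The 35%, 20%, 5% and 40% inputs come from nowhere in the documents. Hiding every exposure is an extreme assumption, especially for a PCR-based assay on extracted DNA (8.1.1, 8.2.4). With the rates in 6.1.2 and the treatment shares assumed for them, the association weakens but does not reverse.
- **Remedy.** A woman whose infection has been cleared by treatment will still read negative after a 3-day deferral, so exclusion alone does not remove the masking modelled above.

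None of this closes the gap in the criteria. It limits what may be claimed about its effect.

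**Conclusion.** The gap is real. As written, recent non-antibiotic vaginal medication, douching and transvaginal procedures do not affect eligibility in either group, and the status of vaginal antibiotics depends on one ambiguous word. The protocol gives its own reason to care about medication and douching, and a weaker one for procedures. Exposure misclassification is therefore possible, and a difference between groups is plausible but undocumented.

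The size and direction of any bias cannot be derived from the documents. The odds ratios above rest on assumed treatment and masking rates and must not be read as estimates of what this study would show. The point justifies a small change before recruitment. It does not show that Part II would give a wrong answer.

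**What to change.** 1. **Criterion, identical in both groups (5.2 and the Program Summary).** Replace the antibiotic exclusion with: *used systemic or vaginal antibiotics or other vaginal medication, used vaginal douching, or had a transvaginal procedure, in the 3 days before the examination*. This keeps the protocol's existing window and removes the doubt about *consumed*.
2. **Deferral.** State that a woman who fails only this criterion may be sampled at a later visit once the window has passed, so that she is not lost. This concerns when the swab is taken and changes nobody's treatment.
3. **Recording.** Add type and date of last use (or of the procedure) to the 8.2.2 form for every participant. This matters as much as the exclusion, because deferral does not undo clearance by earlier treatment.
4. **Analysis.** In section 12, name a sensitivity analysis that uses this record in the planned stratified analysis or logistic regression, and report the frequency of recent local exposure by group.

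The cost is one reworded criterion, a short addition to the form and one sentence in the analysis section. The downside is that a few women are sampled some days later.

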### **5.3 Exit Criteria**

**Case group.**

- 1) Unsatisfactory sample nucleic acid extraction
- 2) Intraoperative detection of developmental malformations or other non-colony related factors that can clearly cause infertility

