#### 6.2 Grouping method

Case group were patients with clinical diagnosis of infertility: sexually active, uncontraceptive and infertile for 2 years

The control group was those with spontaneous pregnancy: those with spontaneous pregnancy at the follow-up visit 3 months after consultation

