### 7. Interventions

This study did not involve an intervention

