8.1.6 Performing diagnostic effectiveness analysis

## **8.2 Part II Assessment of the association between lower genital tract pathogen infection, CST and infertility using newly developed assays**

8.2.1 Select infertile women of childbearing age who meet the criteria for nadir to sign informed consent and be enrolled in the study.

8.2.2 Completion of an information collection form to obtain information on **confounding factors that** may affect this study (age, weight, height, ethnicity, ancestry, place of long residence, number of pregnancies and births, time of last menstruation and menstrual cycle, duration of infertility, relevant diagnoses leading to infertility, etc.), which is collected daily by the information management specialist and kept.

8.2.3 Sample collection: take cervical canal and vaginal secretions during routine gynecological examination and routine leucorrhea examination secretions during routine consultation. ④ Place the swab head in sterile storage solution and tighten the cap ⑤ Label the bottle with patient information ⑥ Store in 4°C refrigerator.

8.2.4 Isolation and extraction of pathogen DNA.

8.2.5 Detection of microorganisms in the lower genital tract by a constructed MALDI-TOF MS assay.

8.2.5 Uniform disposal of remaining specimens in accordance with medical waste after sample testing is completed.

8.2.6 Statistical analysis to assess the correlation between various pathogenic infections and CST status and infertility separately

[figure not shown]
8.2.7 Statistical analysis to assess differences in CST status between infected and uninfected individuals with various pathogens

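### Sections 5.2 and 5.3 disqualify cases on different lists of causes, so whether a woman counts as a case can depend on how her cause of infertility was detected

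*Combined protocol and SAP*

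**What the plan says.** Three parts of the combined protocol and SAP decide who is a case in Part II.

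- **Entry (5.1 and 6.2).** A case must "Conform to the clinical diagnosis of infertility", which 6.2 describes as "sexually active, uncontraceptive and infertile for 2 years". Neither section requires the infertility to be unexplained.
- **Exclusion at entry (5.2, repeated in the Program Summary).** Three items concern the cause of infertility: "Infertility due to malformation of reproductive tract", "Infertility caused by endocrine factors such as polycystic ovary syndrome" (among other endocrine examples) and "Infertility due to male factors". The remaining items are general: tumours, autoimmune disease, severe underlying disease, recent antibiotics, and smoking and drinking.
- **Exit (5.3, case group, item 2).** A case leaves on "Intraoperative detection of developmental malformations or other non-colony related factors that can clearly cause infertility".

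Section 8.2.2 collects "duration of infertility, relevant diagnoses leading to infertility" on the information form, as confounding information. Section 12 lists chi-square and rank sum tests, stratified analysis and logistic regression for Part II. It names no strata or covariates and gives no rule for using the recorded diagnosis to define the case set. No operation on cases is scheduled, and section 7 states: "This study did not involve an intervention".

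**The concern.** Section 5.3 treats any clear non-colony cause as incompatible with being a case. Section 5.2 applies that standard to three kinds of cause only, and 5.3 applies it in full only when the cause comes to light at operation. Between the two rules lies a group of women who have a disqualifying cause by the protocol's own description but whom neither rule removes.

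Part II asks whether infection and CST are related to infertility. Women whose infertility is already explained by something unrelated to the flora add little information on that question. If they look like controls in their exposure, they pull the case rate toward the control rate. How many remain would depend on prior work-up and on who happens to be operated on, and the protocol controls neither.

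**Working it through.** **Step 1: apply the rules as written.** Take a clear non-colony cause outside the three kinds in 5.2, for example tubal damage from earlier non-infectious surgery.

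| How the cause becomes known | 5.2 | 5.3 | Result |
|---|---|---|---|
| Already diagnosed at entry, no operation during the study | not listed | not triggered | kept |
| Found after the swab by a non-operative route | not listed | not triggered | kept |
| Found at operation after the swab | not listed | triggered | removed |

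The cause is the same in all three rows; only the route of detection differs.

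**Step 2: effect on the contrast.** Let q be the share of cases in the first two rows, p1 the exposure rate in the other cases and p0 the rate in controls. Assume the retained women have rate p0.

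- Observed case rate: r = (1-q)·p1 + q·p0
- Difference: r - p0 = (1-q)·(p1 - p0)
- Odds ratio: [r/(1-r)] / [p0/(1-p0)]
- Power: Φ((|r - p0| - 1.96·se0)/se1), with se0 from the pooled rate and se1 from the separate rates, n = 114 per group, two-sided 5%

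The group size of 114 comes from 6.1.2. It cannot be reproduced, because that section gives no alpha, power or interval width for Part II. It serves here only as the group size. Neither q nor a CST exposure rate is in the documents, so both are assumed.

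Worked line for 40% vs 20%, q = 10%:

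- r = 0.9·0.40 + 0.1·0.20 = 0.38; pooled rate 0.29
- se0 = √(0.29·0.71·2/114) = 0.0601
- se1 = √((0.38·0.62 + 0.20·0.80)/114) = 0.0589
- Power = Φ((0.18 - 1.96·0.0601)/0.0589) = Φ(1.06), about 85%

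| q | 40% vs 20%: odds ratio | power | 20% vs 5%: odds ratio | power |
|---|---|---|---|---|
| 0 | 2.67 | 91% | 4.75 | 93% |
| 2% | 2.62 | 90% | 4.66 | 93% |
| 5% | 2.56 | 89% | 4.53 | 91% |
| 10% | 2.45 | 85% | 4.31 | 89% |
| 20% | 2.25 | 77% | 3.89 | 83% |
| 30% | 2.06 | 67% | 3.49 | 75% |

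**Step 3: the plan's own rates.** Section 6.1.2 gives infection rates of 0.01% and 0.46%. The difference of 0.45 percentage points would fall to 0.9·0.45 = 0.405 at q = 10% and 0.7·0.45 = 0.315 at q = 30%. At those rates 114 cases yield an expected 114·0.0046 = 0.52 infected women. Power is about 10% before any dilution and 8% at q = 30%, so these rates cannot usefully illustrate a loss of power. If the figures were meant as proportions (0.01 and 0.46), power stays at practically 100% throughout.

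**The case against.** The strongest reply is that the text permits a mixed case group but does not show one. Once malformation, endocrine, male-factor, tumour, autoimmune and severe-disease patients are excluded, few women with another known cause may remain. At a share of 2% to 5% the loss is at most about 2 power points. This stands: a reader might infer from 5.2 and 5.3 that the case group is a mixture and the contrast is diluted, but the documents give no share and no exposure rate from which to conclude that.

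The direction is also not assured. The background section links lower genital tract infection and abnormal CST to pelvic inflammatory disease and infertility. Some tubal or pelvic diagnoses may therefore lie on the pathway under study, and leaving them off the entry list could be deliberate. This stands as a limit on the dilution argument. It does not explain why 5.3 removes clear non-colony causes by one route of detection only.

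A reader might also take the table as a loss against the planned effect. That does not follow. The 0.46% in 6.1.2 refers to the hospital's infertility patients without a stated restriction by cause, so it may already include such women. The comparison is with a case group defined by one rule.

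It can be said that 8.2.2 and the methods in section 12 already deal with the matter. The data are there, but no rule uses them. Controls have no infertility diagnosis, so adjusting for it as an ordinary covariate cannot work; the case set itself has to be restricted.

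Finally, the exit rule's reference to an operation is undefined. Section 11 uses the word operation in connection with sampling, and on that reading the contrast with surgical patients largely falls away. The two lists of causes would still differ.

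**Conclusion.** The point holds as an inconsistency between two stated rules. Followed as written, 5.2 and 5.3 let the same clear non-colony cause keep one woman and remove another, according to how it was detected.

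The consequence is conditional. If the retained women have about the control exposure rate, the difference shrinks by (1-q). At the assumed 40% vs 20% contrast this is small at q = 5% (91% to about 89% power) and material at q = 30% (about 67%). If the retained conditions are themselves associated with CST, the bias could run either way. The documents settle neither the size nor the direction. To say that the odds ratio refers to no definable case population would go too far: the recorded diagnoses allow a consistent case set, provided a rule for using them is written down. The correction is worth making because it is cheap and applies the protocol's own standard.

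**What to change.** **Preferred:** use one list of disqualifying causes in 5.2 and 5.3, worded as 5.3 already has it (malformation, or any other non-colony factor that can clearly cause infertility). State that it applies whenever and by whatever route the cause is found. Adding the clause to 5.2 alone is not enough, because 5.3 would still act only on detection at operation. Endocrine and male factors can stay as named examples.

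**Alternative, with entry unchanged:** define the main case set for 8.2.6 as cases with no such cause among the diagnoses recorded under 8.2.2. Update those diagnoses with any made before analysis, and have them classified blind to the MALDI-TOF MS result. Report all enrolled cases with a valid sample, including those exited under 5.3 item 2, as a sensitivity analysis.

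**Cost:** a short amendment to 5.2 and 5.3, or a short case-set rule in section 12. The alternative also needs the diagnoses to be kept current after the form is completed, which the plan does not now provide for. Either way the main case set is somewhat smaller, or recruiting 114 cases takes longer.
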